frequent testing to assess for side effects and toxicity. The laboratory assessments would include: Liver Functional Tests (LFTs), Urinary Analysis and any anti-epileptic drug (AED) levels,

- Urine Pregnancy Test (only for women of child bearing potential)
- AEP Questionnaire
- Columbia-Suicide Severity Rating Scale (C-SSRS) Questionnaire
- Conditional Procedure: EEG— an video EEG (30-60 minutes recording) will only be performed at the first follow up study visit where the participant reaches their target dose of CBD, as judged by the clinician. At the discretion of the investigator, an additional EEG may be performed at follow up visits, depending on clinical course.
- Study Drug CBD Medication Order and/or adjustments in CBD dosing (as described under Dosing Adjustment/Schedule section above)

Phone Visit 2/Day 21 (+/-1 day) :

After subject has completed Day 15 through Day 20 (+/-2 days) of CBD medication, the following will be accessed via phone visit 2 with study staff.

- Adverse event and Severe adverse event monitoring/reporting (e.g., increase in seizure frequency by more than 100% leading to emergency room visit or hospitalization)
- Seizure frequency and severity data collected using participant monthly seizure diary, and the Chalfont Seizure Severity Scale.

Phone Visit 3/Day 35 (+/-1 day):

After subject has completed Day 29 through Day 35 (+/-2 days) of CBD medication, the following will be accessed via phone visit 3 with study staff.

- Adverse event and Severe adverse event monitoring/reporting (e.g., increase in seizure frequency by more than 100% leading to emergency room visit or hospitalization)
- Seizure frequency and severity data collected using participant monthly seizure diary, and the Chalfont Seizure Severity Scale.

Phone Visit 4/Day 49 (+/-1 day) :

After subject has completed Day 42 through Day 49 (+/-2 days) of CBD medication, the following will be accessed via phone visit with study staff.

- Adverse event and Severe adverse event monitoring/reporting (e.g., increase in seizure frequency by more than 100% leading to emergency room visit or hospitalization)
- Seizure frequency and severity data collected using participant monthly seizure diary, and the Chalfont Seizure Severity Scale.

Phone Visit 5/Day63 (+/-1 day) :

After subject has completed Day 56 through Day 63 (+/-2 days) of CBD medication, the following will be accessed via phone visit 5 with study staff.

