Subsequent Visits: Study Visit 8/Day 112/Wk 16/Month 4 (+/- 7 days), Study Visit 9/Day 140/Wk 20/Month 5 (+/- 7 days), Study Visit 11/Day 252/Wk 36/ Month 9 (+/- 7 days), Study Visit 12/Day 336/Wk 48/ Month 12, Study Visit 13/Day 420/Wk 72/ Month 18, Study Visit 15/Day 588/Wk 120/ Month 30, Study Visit 16/Day 672/Wk 144/Month 36, Study Visit 17/Day 756/Wk 168/ Month 42:

Procedures for these visits will include:

- Adverse Event and Serious Adverse Event Monitoring (e.g., increase in seizure frequency by more than 100% leading to emergency room visit or hospitalization)
- Seizure Diary Data reviewed and collected by study staff
- Menstrual History collected by study staff
- Chalfont Seizure Severity Scale
- Vital signs: Age, Weight, Height, Heart Rate, and Blood Pressure, Temperature
- Urine Pregnancy Test (only for women of child bearing potential)

- CBC and CMP (collected at SV8, SV9, SV12, SV16 only); Study doctor may order additional laboratory testing (blood and/or urine tests) and/or more frequent testing to assess for side effects and toxicity. The laboratory assessments would include: Liver Functional Tests (LFTs), Urinary Analysis and any anti-epileptic drug (AED) levels,
- Physical and Neurological Examination
- Columbia-Suicide Severity Rating Scale (C-SSRS)
- AEP Questionnaire
- NIH Toolbox for Emotional Assessment**: Emotion Measures from the NIH Toolbox will be administered to each participant and/or their legal guardian. The Emotion Measures from the NIH Toolbox assess four major domains: Negative Affect (NA), Psychological Well-Being (PWB), Social Relationships (SR), and Stress/Self-Efficacy (SSE). ****Performed at Study Visit 12/Day336/Wk48/Month 12 only****

For participants ages 3 – 7, the following age-appropriate subtests from the NIH Toolbox Emotion Parent Proxy Battery will be administered:

- Negative Affect
 - o NIH TB NA Anger – Parent Report
 - o NIH TB NA Fear-Over Anxious Parent Report for Children
 - o NIH TB NA Fear-Separation Anxiety Parent Report FFSF
 - o NIH TB NA Sadness Parent Report FFSF for Children
- Psychological Well-Being
 - o NIH TB PWB General Life Satisfaction Parent Report SF-FF
 - o NIH TB PWB Positive Affect Parent Report CAT
- Social Relationships
 - o NIH TB SR Empathic Behaviors Parent Report CAT
 - o NIH TB SR Peer Rejection Parent Report FFSF
 - o NIH TB SR Positive Peer Interaction Parent Report FFSF
 - o NIH TB SR Social Withdrawal Parent Report FF-SF

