## Statistical Analysis Plan

The UAB Pediatric CBD Program enrolled 89 treatment resistant epileptic children ages 1-19 years old. All study participants received Epidiolex drug (Cannabidiol; CBD) as an add-on to their previously stable anticonvulsive treatment after baseline assessment. Participants received a starting dose of CBD at 5 mg/kg/day in twice daily dosing and titrated by 5 mg/kg/2 weeks up to 25 mg/kg/day, with a maximum dose of 50 mg/kg/day. Seizure frequency, severity, and adverse events together, with other clinical participant measures, were assessed at baseline and bi-weekly for the duration of the study.

The first 12-months (1-year) of follow-up data were analyzed as follows:

1. The primary outcome measures included:

- a. Severe adverse events (increase in seizure frequency by more than 100% leading to emergency room visit or hospitalization),
- b. Change in resting blood pressure or heart rate by 25% if considered significant by managing neurologist,
- c. Any change in, CBC, CMP, Liver function tests (LFTs), Urinary Analysis or Antiepileptic drug (AED) levels considered by managing neurologists as clinically significant. Clinically significant will be determined by using the Common Toxicity Criteria for Adverse Events (CTCAE) Version 4.03. Adverse events (AE) categorized as a grade 3 or above will be considered clinically significant. Adverse Events graded 4 or above will be considered severe adverse events (SAE).

The analysis plan was focused on safety. The information on safety was tabulated as the percent of participants with each safety outcome AE and SAE, or others reported as meaningful as well as the number of occurrences of each AE and SAE. This enabled an event rate calculation per exposure time as well as the average number of occurrences per participant with an AE or SAE.

2. The secondary analysis assessed the frequency and severity of seizure outcome measures to include:

- a. Mean (SD) and median (IQR) decrease in seizure frequency as measured in total number of seizures per month.
- b. Mean (SD) and median (IQR) decrease in seizure severity as measured by the Chalfont Seizure Severity Scale (Duncan & Sander, 1991, JNNP).

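### The SAP's 12-month adverse event rate pools periods with very different contact schedules, and its statement that assessment was bi-weekly throughout contradicts the protocol; rates should be reported by period

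*Protocol*

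**What the plan says.** The SAP opens its analysis section with "The first 12-months (1-year) of follow-up data were analyzed as follows". For safety, "The information on safety was tabulated as the percent of participants with each safety outcome AE and SAE", together with the number of occurrences, and it adds: "This enabled an event rate calculation per exposure time". It gives no division by time, dose or phase of treatment. Its opening paragraph says that seizure measures, adverse events and other measures "were assessed at baseline and bi-weekly for the duration of the study".

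The protocol's visit descriptions and Schedule of Events set out a different pattern. During standard titration a phone visit alternates with a clinic visit, so contacts are a week apart until Study Visit 6 on Day 70. Study Visits 7 to 10 follow on Days 84, 112, 140 and 168. The rest of the first year has "Study Visit 11/Day 252/Wk 36/ Month 9 (+/- 7 days), Study Visit 12/Day 336/Wk 48/ Month 12" and no phone visit. Children taken above 25 mg/kg/day have visits every 2 weeks while the dose is raised, and their later visits are moved accordingly.

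The protocol's Data Analysis section also plans Kaplan-Meier summaries of time to onset for adverse events seen in at least 10% of participants. The SAP does not carry this over.

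**The concern.** A single rate per exposure time is a fair summary when a child-day means much the same thing throughout follow-up. Here it does not. A day in the first ten weeks is usually spent on a rising dose with weekly questioning. A day in month 8 is usually spent at a maintained dose with questioning 12 weeks apart. The pooled rate averages the two.

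It also depends on who stays. The protocol (Participant Recruitment) sets no minimum duration and lets participants stop at any time, so early leavers add only closely watched titration time. A reader told that assessment was bi-weekly throughout has no reason to suspect any of this.

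Safety is the primary aim of the study. With the Kaplan-Meier analysis gone, no safety summary in the SAP shows when events occur.

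**Working it through.** **Plan's own figure.** The documents give no precision figure for the event rate. The only one for safety is the half-width of a two-sided 90% interval for a proportion at N = 100. It reproduces: 1.645 × √(p(1−p)/100) = 0.049, 0.066, 0.075, 0.081 and 0.082 for p = 0.10 to 0.50. It says nothing about the rate.

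**Contacts.** Days 7, 14, 21, 28, 35, 42, 49, 56, 63, 70, 84, 112, 140, 168, 252 and 336 make 16 after Day 0. The gaps are ten of 7 days, one of 14, three of 28 and two of 84. Child-time is for the 89 enrolled, assuming no dropout: 89 × days / 365.25.

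| Period | Contacts | Share of 336 days | Contacts per 28 days | Child-years |
|---|---|---|---|---|
| Days 0-70 | 10 | 20.8% | 4.0 | 17.1 |
| Days 71-168 | 4 | 29.2% | 1.14 | 23.9 |
| Days 169-336 | 2 | 50.0% | 0.33 | 40.9 |

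4.0 / 0.33 is a 12-fold range.

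**Loss between contacts (assumed model).** Suppose the chance that a non-serious event is reported at the next contact halves every H days. The share captured over a gap of L days is c = (1 − exp(−kL))/(kL), with k = ln 2 / H. If a fraction s is reported spontaneously and fully captured, the share is s + (1 − s)c. The table shows the apparent fall from Days 0-70 (L = 7) to Days 169-336 (L = 84) when the true rate is constant.

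| H | c at L = 7 | c at L = 84 | s = 0 | s = 0.5 | s = 0.8 |
|---|---|---|---|---|---|
| 28 days | 0.918 | 0.421 | 54% | 26% | 10% |
| 56 days | 0.958 | 0.622 | 35% | 17% | 7% |
| 84 days | 0.972 | 0.721 | 26% | 13% | 5% |

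For example, with H = 28 and s = 0.5: 1 − (0.5 + 0.5 × 0.421)/(0.5 + 0.5 × 0.918) = 1 − 0.710/0.959 = 26%.

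**Direction for the pooled rate.** Let the true rate in Days 0-70 be R times the later rate. The recorded pooled rate, relative to the true later rate, is (70·R·c₁ + 98·c₂ + 168·c₃)/336, where c₁ to c₃ are the captured shares by period. Over H = 14 to 180 days and s = 0 to 0.8:

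- R = 1: 0.46 to 0.98
- R = 3: 0.81 to 1.40
- R = 5: 1.16 to 1.81

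The sign changes at some R between 1.09 and 4.07, depending on H and s.

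**Dependence on leaving.** Take R = 3, full capture, and a fraction d leaving at Day 70. The pooled rate in later-rate units is (210 + 266(1 − d))/(70 + 266(1 − d)):

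- d = 0: 476/336 = 1.42
- d = 0.25: 409.5/269.5 = 1.52
- d = 0.5: 343/203 = 1.69

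A single child leaving at Day 70 contributes a rate of 3.0. R and d are assumptions.

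**Measured outcomes.** Blood pressure, heart rate and laboratory changes are not found by phone. Clinic visits after Day 0 number 5, 4 and 2 in the three periods. Scheduled CBC and CMP number 2 (Days 28 and 56), 4 (Days 84, 112, 140 and 168), and then 1 or 2. The Subsequent Visits list omits Study Visit 11, leaving only Day 336. Footnote e to the Schedule of Events includes the 9-month visit.

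**Titration above 25 mg/kg/day.** Under Dosing Adjustment/Schedule, 25 mg/kg/day starts at Week 9, that is Day 57. Five further 2-weekly steps to the protocol's maximum run to about Day 57 + 5 × 14 = 127. For these children calendar periods do not separate titration from maintenance.

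**The case against.** **Capture does not rest on scheduled contacts alone.** Families can reach staff at any time, spontaneous reports count as adverse events, and side effects or more seizures can prompt an unscheduled visit. This stands and matters: it cuts the apparent fall from 26-54% to 13-26% if half of events are spontaneously reported, and to 5-10% if 80% are. It does not remove the fall. The first listed primary outcome, seizure worsening leading to an emergency visit or admission, is probably little affected; that is judgement.

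**The rate is not the headline figure.** The SAP lists the percent of participants first, and the protocol's only safety precision statement is for a proportion. That stands. That the rate is a single pooled one is also inferred from the SAP's silence about periods.

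**Stronger readings.** A reader might infer that the pooled rate understates risk in long-term use. The documents do not support a direction. Lost reports pull the rate down, but including titration can push it above the later rate; at R = 3 with full capture it is 1.42 against 1. A reader might also infer that the plan as written would make tolerance appear to grow. One pooled number cannot fall over time. That risk arises only once the rate is split, which is why the split needs a caution.

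**Conclusion.** The concern holds as a reporting weakness and a factual inconsistency. Two things rest on the documents alone. The SAP's description of assessment frequency is contradicted by the protocol's 28-day and 84-day gaps. The rate, as described, combines periods with a 12-fold difference in scheduled contacts on standard titration, without saying so.

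The size and sign of the resulting error are not known. They depend on recall, spontaneous reporting, early clustering and dropout, and the documents give figures for none of these. The ranges above show what is possible under assumed values and are not estimates. The recall model applies to non-serious symptoms. For vital signs and laboratory values what matters is the visit and laboratory dates, and the two statements on Month 9 laboratory tests must be reconciled before the density of those measurements can be stated.

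This is a worthwhile, inexpensive improvement. It does not show that the safety results are wrong.

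**What to change.** 1. In the SAP, replace the bi-weekly statement with the actual contact intervals, including the shifted 2-weekly schedule above 25 mg/kg/day. Reconcile footnote e with the Subsequent Visits list on Month 9 laboratory tests.
2. Report events, child-time and rate with an interval for Days 0-70, 71-168 and 169-336, or by titration and maintenance for each child. State the contact interval and the laboratory interval for each period. Keep the pooled rate as a secondary line.
3. Add a note that a fall between periods may reflect less frequent questioning and is not in itself evidence of tolerance.
4. Restore the Kaplan-Meier time-to-event analysis from the protocol, or explain why it was dropped. It covers only time to onset of common events, so it does not replace the rates by period.

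The cost is SAP wording and extra table columns. No new data are needed if onset dates are held, which the recording of event duration and the planned time-to-event analysis imply but no passage states outright. The SAP is written in the past tense, so the split should be labelled as an added descriptive analysis.

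The downside is precision. With a constant recorded rate, Poisson counts and no dropout, relative interval widths grow by about 1/√0.208 = 2.2, 1/√0.292 = 1.9 and 1/√0.5 = 1.4 times against the pooled interval.

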Seizure Frequency through Diary Data Collection			X	X	X	X
NIH Emotional Measures or Bayley Emotional Scales ^d			X			
Social Determinants of Health data collection			X			
Titrate CBD (if needed)					X	X
Dispense Medication			X		X	X
AE/SAE Monitoring/Reporting				X	X	X

UAB CBD Program: Children's Protocol Schedule of Events (Patients 1 years to 18 years of age) -Page 3 of 5

Activities/Procedures:	SV7/Day 84 (+/- 3 days) or Follow up study visit 28 days after after Target dose is reached:	SV10/Day168/Wk 24/Month 6 (+/- 7 days), SV 14/Day 504/Wk 96/Month 24 (+/- 7 days), SV18/Day 840/Wk 192/Month 48 (+/- 7 days):	SV8/Day 112/Wk 16/Month 4 (+/- 7 days), SV9/Day140/Wk 20/Month 5 (+/- 7 days), SV11/Day 252/Wk 36/ Month 9 (+/- 7 days), SV12/Day 336/Wk 48/ Month 12, SV13/Day420/Wk72/ Month 18, SV15/Day 588/Wk 120/ Month30, SV16/Day 672/Wk 144/Month 36, SV17/Day 756/Wk 168/ Month 42:	Unscheduled Visit or Early Termination Visit (prior to year 1 visit):	Post-Termination Study Visit (approximately 28 days after CBD wean):
Seizure Frequency through Diary Data Collection	X	X	X	X	X
Chalfont Seizure Severity Scale	X	X	X	X	X
Neurological Exam	X	X	X	X	X
General Physical Exam	X	X	X		
Laboratory Assessments ^e	X ^e	X ^e	X ^e	X ^e	X ^e
Electrocardiogram (ECG)				X (at early term visit prior to year 1 only)	X
Urine Pregnancy Test (only for women of child bearing potential)	X	X	X	X	X
Menstrual History Data	X	X	X	X	X
EEG ^a (30-60 minute) duration	X	X ^a	X ^{a,g}	X ^c	
Vital Signs (age, weight, height, HR, BP,	X	X	X	X	X
Pediatric Cognitive Testing (NIH Toolbox), ABAS-II or Bayley Functional Scales ^b		X		X ^c	
Quality of Life in Childhood Epilepsy (QOLCE)		X		X ^c	
Adverse Events Profile	X	X	X	X	X
Columbia Suicide Severity Rating Scale (C-SSRS)	X ^a	X	X	X	X
Child Behavioral Checklist Assessment	X	X			
NIH Emotional Measures or Bayley Emotional		X (SV10 only)	X (SV12 only)		
Social Determinants of Health data collection		X		X ^c	
Titrate CBD (if needed)	X	X	X	X	
Dispense Medication	X	X	X	X (if needed)	
AE/SAE Monitoring/Reporting	X	X	X	X	X

X* =Participants' who have an Enrollment Visit and Study Visit1/Day 0 conducted on the same day will have the following activities performed only once during the visit: Urine Pregnancy test, Seizure Frequency Calendar, Chalfont Seizure Severity Scale, Neurological Exam, General Physical Exam, and Vital signs.

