
(Bayley-III®)-Emotional Assessments will be completed by the parent or LAR of the participant, instead of the NIH Emotional Measures assessments.

^e Laboratory Assessments collected at Study Visit 1 will include a CMP and CBC. The study doctor may order additional laboratory testing (blood and/or urine tests) at follow up study visits to assess for side effects and toxicity. The laboratory assessments would include: CMP, CBC, Liver Functional Tests (LFTs), Urinary Analysis and any anti-epileptic drug (AED) levels). Subjects approved for the UAB CBD Open Access Program must have laboratory studies within 3 months of the committee review which include: CBC, Complete Metabolic Panel, Urine Analysis and anti-epileptic drug levels. If the subject enrolls in the program and completes the screening visit within 3 months of the required baseline laboratory studies, they are not repeated at Study Visit #1. If the subjects enrolls outside the three month window, the laboratory studies are repeated (CBC, CMP, anti-epileptic medication levels) at Visit #1. During the initial 3 months of the titration of CBD up to 25 mg/kg/day (study visit every 2 weeks), repeat laboratory studies will be done at 4-week intervals until the 6-month visit and then every 3 months (9-month and 12-month visit) and then at 6-month intervals for the duration of the study. At each visit, complete vital signs are taken and review of potential adverse events and menstrual history will be done. If there is any concern of the anti-epileptic medication interaction with CBD, additional AED levels are drawn at the study visit. Particular attention is given if the subject is currently taking valproic acid and clobazam because of potential drug interactions. A urine analysis is completed at Study Visit #1 and will be completed as needed throughout the protocol to monitor for toxicity or potential side effects. A urine analysis schedule will be added at 3-month intervals during the first year of the study and every 6 months for years 2 and 3. An ECG is obtained as part of the screening process, but will be repeated at 6 months, 12 months and then yearly while participants are enrolled in the study. The early discontinuation visit will include a CBC, CMP, UA and an ECG.

^f Patients have the option of participating in an fMRI Substudy.

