^g An EEG will be performed at the first annual (12 month) study visit. If participant has already pasted this visit, the EEG will be performed at their next study visit.

CRFs for this program were created using the NINDS common data elements CRFs and other common Epilepsy data collection resources.

Withdrawal of Participant Consent and Early Termination/Discontinuation of Study Drug:

Study participation may be discontinued for any of the following reasons:

- Administrative decision by the investigator or GW Research Ltd or Regulatory Authority.
- Subject decision to withdraw consent/assent for study.
- Withdrawal of parent/legal authorized representative consent.
- Pregnancy.
- Evidence of allergy to administered products.
- Lost to follow up
- Patient non-compliance
- Protocol deviation that is considered to potentially compromise the safety of the patient.
- In Investigator's judgement, development of active medical condition/treatment that impacts study activities.
- Intolerable adverse event as judged by study investigator and participant.
- Serious Adverse Event, which in the investigator's opinion compromises the safety of the patient.
- ALT or AST >8xULN
- ALT or AST >5xULN for more than 2 weeks
- ALT or AST >3xULN and (TBL >2xULN or INR >1.5)
- ALT or AST >3xULN with the appearance of fatigue, nausea, vomiting, right upper quadrant pain or tenderness, fever, rash, and/or eosinophilia (>5%)
- For any clinically significant (> 3 x ULN) elevation of ALT or AST in children under 21 years of age being treated with Epidiolex in an Expanded Access IND, the following laboratory measures, at minimum, should be assessed within 72 hours: repeat ALT/AST, total bilirubin, alkaline phosphatase, and GGT.
- All trial subjects with elevated LFTs should be followed until all abnormalities return to the baseline state as assessed by the investigator with AST/ALT < 3X ULN.
- If a subject has elevated LFTs (>3x ULN) and is on valproic acid the subject must stop the CBD and the LFTs must be monitored until the return to baseline state. If the subject has shown an improvement in their seizure frequency with the addition of CBD the option to "rechallenge" CBD will be at the discretion of the study PI. It would require that the subject taper off valproic acid and be on a stable dose of antiepileptic medication for 30 days prior to restarting the CBD. They would have repeat baseline labs (CBC, CMP and AED levels) prior to restarting the CBD.

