This visit may be combined with the Enrollment Visit. It must occur within 30 days of the enrollment visit.

Procedures for Study Visit 1 include:

- Seizure Calendar or Diary Data reviewed and collected by study staff
- Menstrual History collected by study staff
- Adverse event and serious adverse event monitoring (e.g., increase in seizure frequency by more than 100% leading to emergency room visit or hospitalization)
- Chalfont Seizure Severity Scale
- General physical and neurological Examination
 - To be performed by the study physician at each visit
- Vital Signs: Age, Weight, Height, Heart Rate, and Blood Pressure, Temperature
- Complete Blood Count (CBC), and Comprehensive Metabolic Panel (CMP)
- Electrocardiogram (ECG) and Urinary Analysis (UA) collected by the study staff (completed as needed throughout the protocol)
- AED levels
- Urine Pregnancy Test (only for women of child bearing potential)
- Columbia-Suicide Severity Rating Scale (C-SSRS) Questionnaire
- Child Behavioral Checklist for participants between ages 1-18 years old

- Pediatric Cognitive performance testing (NIH Toolbox; performed at study visit 1 and annually) – NIH Toolbox is a multidimensional set of royalty-free measures that researchers can use to assess cognitive, sensory, motor and emotional function in people ages 3-85. This suite of measures can be administered to study participants in two hours or less, across diverse study designs and settings. The measures have been normed and validated in a broad sample of the U.S. population. For this study, the Cognitive subtests from the NIH Toolbox will be administered. These tests are designed to have a wide range of utility with people with varying levels of cognitive capacity, but for those participants who are unable to complete the cognitive tests from the NIH Toolbox, parent-report measures pertaining to functional adaptive status will be administered.

For participants ages 3-6, these measures from the NIH Toolbox include:

- NIH Toolbox Dimensional Change Card Sort Test (DCCS) – cognitive flexibility
- NIH Toolbox Flanker Inhibitory Control and Attention Test – attention and inhibitory control
- NIH Toolbox Picture Sequence Memory Test – episodic memory
- NIH Toolbox Picture Vocabulary
- NIH Toolbox Oral Reading Recognition Test (for children who have developed letter and/or word recognition skills)

For participants ages 7-18, these measures from the NIH Toolbox include:

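### The Subsequent Visits list omits the month-9 CBC/CMP that schedule footnote e requires, so scheduled liver enzymes have a 24-week rather than a 12-week gap in year 1

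*Protocol*

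**What the plan says.** **Blood tests.** Footnote e to the Schedule of Events spaces repeat laboratory studies four weeks apart "until the 6-month visit and then every 3 months (9-month and 12-month visit) and then at 6-month intervals". In the follow-up table, the laboratory row carries a pointer to footnote e in the column whose header includes "SV11/Day 252/Wk 36/ Month 9 (+/- 7 days". The procedure list headed Subsequent Visits covers the same visit but says "CBC and CMP (collected at SV8, SV9, SV12, SV16 only". The same bullet lets the study doctor order "more frequent testing to assess for side effects and toxicity".

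**ECG.** Footnote e says that the ECG "will be repeated at 6 months, 12 months and then yearly while participants are enrolled in the study". The table's ECG row holds only "X (at early term visit prior to year 1 only" and a mark at the post-termination visit. The SV10 and SV12 lists contain no ECG. The Study Visit 1 list has "Electrocardiogram (ECG) and Urinary Analysis (UA) collected by the study staff (completed as needed throughout the protocol".

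**Urinalysis.** Footnote e leaves it to clinical need in one sentence and adds a three-monthly schedule for the first year in another. The lists for SV7, SV10, SV11 and SV12 make it an optional order by the study doctor.

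**Cognition and social determinants (SDH).** The text promises cognitive testing at Study Visit 1 and then yearly, and SDH reassessment at year 1. The table and lists place both at SV10 (month 6) and not at SV12 (month 12).

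**Analysis.** Primary outcome 1c in Data Analysis covers CBC, CMP, liver tests, urinalysis and antiepileptic drug (AED) levels. The SAP repeats it, analyses the first 12 months, and tabulates percentages of participants.

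**The concern.** A coordinator usually books tests from the visit list. Here the list does more than stay silent on month 9: it names four visits and closes the set. The protocol thus gives two incompatible instructions for the same visit.

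What is at stake is detection of liver-enzyme rises without symptoms. The discontinuation criteria, such as "ALT or AST >5xULN for more than 2 weeks" and the mandatory stop for children on valproic acid above 3 times the upper limit, can act only on a result. The omitted draw also lies inside the SAP's analysis window and feeds a primary outcome.

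The other mismatches matter less. Urinalysis and AED levels are in outcome 1c, so discretionary testing may under-count events there. ECG is safety monitoring and appears in no aim, outcome or SAP analysis. Cognitive effects are named in the aims, but Data Analysis treats those data as exploratory and the SAP specifies no analysis of them.

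**Working it through.** The plan states no figure to reproduce, so the check compares the two schedules.

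**1. Are the visit labels reliable in year 1?** Day divided by 7 should equal the week label: SV10 168/7 = 24, SV11 252/7 = 36, SV12 336/7 = 48. All agree. From SV13 on they do not (420/7 = 60 against a label of week 72), so nothing is claimed after month 12.

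**2. Nominal on-treatment CBC/CMP draws in year 1**

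| Source | Weeks | Draws | Longest gap |
|---|---|---|---|
| Footnote e | 4, 8, 12, 16, 20, 24, 36, 48 | 8 | 36 − 24 = 12 weeks |
| Visit lists (SV3, SV5, SV7, SV8, SV9, SV10, SV12) | 4, 8, 12, 16, 20, 24, 48 | 7 | 48 − 24 = 24 weeks |

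The only difference is SV11. This takes footnote e's laboratory studies to include CBC and CMP, which the footnote names for baseline, and assumes that the CMP contains ALT and AST.

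**3. Does the extra target-dose visit fill the gap?** The protocol adds a visit with SV7 procedures, including CBC/CMP, 28 days after target dose if that dose is reached before or after SV6. The counts of 7 and 8 leave it out. Titration without delay reaches 25 mg/kg/day after Day 56. Five further two-week steps to 50 mg/kg/day end at 56 + 5 × 14 = Day 126, and the extra visit falls at 126 + 28 = Day 154, or week 22. It therefore does not close the gap from week 24 to week 48 unless titration is slowed or visits are shifted.

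**4. Illustration only.** Suppose a symptomless rise begins at a uniformly random time between weeks 24 and 48, lasts d ≤ 12 weeks, and no discretionary test is done. The documents give neither the durations nor the onset pattern. Scheduled draws catch it with probability d/24 under the lists and 2d/24 under footnote e.

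| d (assumed) | Lists | Footnote e |
|---|---|---|
| 4 weeks | 4/24 = 17% | 8/24 = 33% |
| 8 weeks | 8/24 = 33% | 16/24 = 67% |
| 12 weeks | 12/24 = 50% | 24/24 = 100% |

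For a rise that persists, mean delay to detection is 24/2 = 12 weeks against 12/2 = 6 weeks.

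**5. Other items, year 1**

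| Item | Promised in footnote e or text | Fixed in the routine visit lists |
|---|---|---|
| ECG, months 6 and 12 | 2 | 0 |
| Urinalysis, months 3, 6, 9 and 12 | 4 | 0 |
| Cognition and SDH, month 12 | 1 each | 0 |

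Layout does not explain the last row: the table marks the emotional measures for SV12 alone within that shared column. Participant Compensation and Costs calls Study Visit 10 the month-12 visit, which suggests that visit numbers were not updated.

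**The case against.** The strongest reply is that footnote e is part of the table. The laboratory marks at SV7, SV10, SV11 and SV12 refer to it, and it orders the month-9 bloods, both ECGs and the urinalyses. The 12-month EEG works this way too: footnote g orders it, while the SV12 list shows only the conditional EEG. A site reading the whole protocol would have every test. This stands for items on which the lists are merely silent. It does not rescue CBC/CMP, where the list confines the draw to four named visits.

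Several stronger readings are tempting and should not be drawn:

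- That the lists contradict the schedule throughout. The tick-box table agrees with the lists on ECG, cognition and SDH. On those items the tension is with the footnote and the frequency wording.
- That children went unmonitored from week 24 to week 48, or that 89 draws were lost. Nothing shows that any child missed the draw. Extra tests may be ordered, and unscheduled visits include CBC and CMP.
- That an untested child is counted as event-free. The protocol and SAP give percentages of participants but state no rule for untested children, and they also provide a rate per exposure time.
- That year-1 cognition is certainly missing. Footnote c hints at collection at the year-1 visit, though too vaguely to settle it.

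Footnote e also accepts six-month laboratory gaps after month 12, so the protocol does not regard such a gap as unsafe in itself.

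**Conclusion.** The month-9 conflict is real and should be corrected. It concerns one CBC/CMP draw, at SV11, and widens the longest scheduled gap in year 1 from 12 to 24 weeks on the nominal calendar. It matters because liver tests are in the primary safety outcome and the gap lies within the 12 months analysed. The loss is confined to rises that produce no symptoms and prompt no discretionary test. The detection percentages rest on assumed durations and should not be cited as the size of the problem.

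The ECG, urinalysis and cognition/SDH mismatches are lesser reconciliations. Urinalysis is unsettled within footnote e itself, ECG enters no outcome, and cognition is exploratory.

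The SAP is written in the past tense, with 89 children enrolled and the first year analysed. For year 1, what remains is to report who was tested.

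**What to change.** **Main change.** Add SV11 to the CBC/CMP bullet under Subsequent Visits and state that footnote e governs where it differs from a visit list.

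**In the same amendment:**
- List ECG at SV10 and SV12.
- Decide between three-monthly and discretionary urinalysis. If three-monthly, remove the discretionary wording from footnote e and the Study Visit 1 list, and enter the test at SV7, SV10, SV11 and SV12.
- List cognition and selected SDH at SV12, moved from SV10 or added to it.
- Test children already past SV12 at their next visit, as footnote g does for EEG.
- After month 12, reconcile the day labels with the week and month labels before changing any draw.

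**Reporting.** For outcome 1c, give the number of children tested for each analyte beside the number of participants. Where records allow, separate scheduled tests from those ordered on suspicion.

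**Cost.** A protocol amendment, and per child one draw, four urinalyses and two ECGs, all already promised in footnote e. Blood and urine tests are billed to insurance, or to the family if insurance does not pay. Moving cognition adds no test but loses the month-6 value; keeping both adds one session of under an hour. Reporting the numbers tested needs no new data collection if the test records are complete.
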